2. Estimate the degree to which expressive nonverbal capacity predicts the social self-management trajectory. Hypothesis: People with PD with higher expressive capacity at baseline will have more positive social trajectories over time than people with less expressive capacity.
3. Determine the moderating effect of gender on the association between expressive capacity in PD and change in social self-management. Hypothesis: Gender will moderate the association. The social trajectories of women are expected to be more vulnerable to the influence of expressive disability than the trajectories of men.

Methods/design

Research design

This prospective cohort study design tracks general patterns of the sample as a whole as well as variation among individual trajectories in social self-management. The tracking creates evidence necessary to develop social life interventions that address the typical issues faced by people living with the disease as well as individual variations in needs. Over a 3-year period, the study plans to follow 120 individuals with PD and their

associated primary care partner. Individuals with PD are included whether or not they have an identified care partner.

There are seven full assessments of approximately two hours duration and in-person, one at baseline and one every six months thereafter, with six in a clinical research lab and one in the home. Between the 6-month full assessments, there is an additional brief telephone call (15 to 30 minutes), totaling seven phone calls over three years. This innovative design of 14 assessments over the three years aims at detecting social or health triggers that affect individual participant's trajectories [4]. Frequent points of contact, while also building statistical power, increases the possibility of capturing remembered details of daily life that send health patterns into non-linear trajectories, such as anniversaries, retirement, bad colds or significant family events [5,6].

Ethics review

Recruitment, consent and data collection protocol have been approved by Social, Behavioral & Educational Institutional Review Board of Tufts University Medford Campus (protocol # 1212038), and the Boston University Medical Campus (BUMC) Institutional Review Board (protocol # H-32114).

Participants

Recruitment

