1. **Social network composition, contact and exchange.** At every visit, a set of items is used that discriminate cultural differences in social networks [20], including having a spouse or partner in the household, number and composition of individuals living in the household, total number of children and total number of grandchildren. Network contact is measured by frequency of contact with the most contacted child, with the most contacted friend, and with the care partner (if not the most frequently contacted child or friend). Social exchange is rated from 1 (very little) to 5 (a large amount) on 18 items. Nine of these items rate the amount of support received in three domains—help with daily activities, emotional support, and financial support—from each of three sources, if applicable: the other study participant (care partner or person with PD), other members of the household, and social network members outside of the household. The other nine items rate the amount of support given by the participant to the other care participant, other household members and others outside of the household, if applicable.

2. Social resources. At every visit, a modified version of the 22-item Chronic Illness Resource Survey (CIRS) assesses quality, composition and use of personal coping resources, informal social resources (e.g., family, friends, neighborhood, community) and formal social resources (health care team, work, organizations, and media/policy). There are nine sub-scores and a total score assessing resource support. For this study, wording is modified slightly to encompass resources commonly available to people with PD (e.g., Parkinson's support groups). The participant with PD and the care partner and respond to parallel forms that changed the wording of "chronic illness" to "health management" to make the questionnaire applicable for both. The original CIRS measure was validated on two large samples of community-living adults with a variety of illnesses and met all standards for psychometric soundness [21,22]. It is sensitive to change over a 1-year period and has provided findings useful for developing interventions.

3. Home visit. One assessment, scheduled approximately 1.5 years into the study, is in the home of each participant with PD. The modified CIRS was used by the interviewer to guide an audiotaped conversation about potential facilitators and barriers in the home and neighborhood environment that may affect social self-management.

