bodily discomfort. A higher score indicates a higher self-perceived frequency of quality of life and health problems in the past month that are due to the disease, with 0 indicating *never a problem* and 100 *always a problem*. The index and domain scores have adequate internal consistency, convergent validity with health status and quality of life measures, test-retest reliability, and responsiveness to intervention. The exception is the social support scale which has weak psychometric properties [34]. The PDQ-8 summary index is a short form of the PDQ-39 that is administered in place of the PDQ-39 for approximately half of the in-person assessments to allow for time to administer the MDS-UPDRS once per year. The PDQ-8 provides adequate psychometrics for detecting minimally important differences in change in health status of PD over a 1-year period [32].

- The MDS-UPDRS is a widely-used clinical assessment and research tool for assessing motor and non-motor symptom severity [33]. Parts I and II assess self-reported non-motor and motor aspects of daily living. Parts III and IV assess observed motor capacity and extent of abnormal movement and are the primary measures for this project. This assessment is administered once per year.

Brief telephone assessments

Calls are scheduled to interview the participant with PD and the care partner separately. The primary objective of these calls is to help inform findings relative to shifts in social trajectories. Participants have the opportunity to elect an alternate means of assessment, such as a mailed questionnaire, if a telephone assessment is perceived as burdensome. It has been found that telephone assessments that occur between

scheduled in-clinic visits are welcomed by people with PD [35], who typically do not find them burdensome, and experience them as comforting, positive attention. The 15- to 30-min audiotaped protocol involves the following assessments:

1. Recent important life events, changes in physical and mental health, and medication changes since the previous assessment,
2. PDQ-8 (administered only to the participant with PD),
3. Social Isolation domain-NHP,

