social isolation score, 6) positive interaction with partner score, 7) felt stigma and enacted stigma scores (SSCI), 8) physical and mental health scores (SF-12), 9) health quality of life with PD scores (PDQ-39 or PDQ-8), and 10) motor capacity scores (MDS-UPDRS, Parts III and IV). Outcomes measured at all 14 time points are: 1) physical and mental health scores (SF-12), 2) health quality of life with PD score (PDQ-8), and 3) loneliness score (Social Isolation, NHP). Temporal dynamics of these outcomes will be explored in order to better understand the similarities, differences and factors governing such dynamics. By including random effects, the population trajectory and the degree of variations of individual trajectories will be explored. Outcomes reported by both the person with PD and the care partner will depict both perspectives, which enable an assessment of the synchronicity between the two sources. Statistical tests of interaction terms will evaluate whether particular factors affect the ratings of one source more than another.

The multilevel models can accommodate subjects with and without care partners, as well as incomplete data collection, as long as data are missing at random [49]. For sensitivity analyses pattern mixture models are used to account for the possibility of informative missingness. The models will stratify by pattern of and reason for missing data [50].

Effects of triggers on trajectories: Exploratory analysis

For exploratory purposes, the general multilevel modeling approach is expanded to consider potential effects of unanticipated triggers assessed at the individually identified time points [4]. The timing of measurements will be calibrated as “time elapsed since an event” or “time preceding an event”. Recalibration enables synchronization of triggering

events across the cohort, allowing determination of synchronized changes in one of the outcomes of interest after occurrence of an unanticipated event. For example, there may be an increase in loneliness following hospitalization of a spouse or a decline in social activity following an episode of physical illness.

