Non-linearities with non-parametric fitting will be explored if a sufficient number of subjects have experienced a similar event. For example, some social triggers may have a temporary U-shaped trajectory. This description of potential rapid or unexpected changes in the trajectories is highly innovative for research in the social aspects of PD and other chronic degenerative conditions. Adding trigger event monitoring to the research design builds power for repeated measures, and it may illuminate the understanding of disease progression as a social ecological phenomenon.

Aim 2: Expressive nonverbal capacity as predictor

Analysis will start with a simple linear model, considering a random intercept and slope for each individual. The assumption is that, the variation among individuals in the intercept and slope of their trajectories can be explained by subject characteristics, including expressive capacity at baseline. For example, it may be found that the rate of change in the study outcomes may vary and depends on expressive capacity at baseline. This preliminary step will guide the further model building.

Multivariate models are built by first adding demographic factors, then clinical factors, and then other variables of interest including masking, life stage, and access to support. The number of variables are reduced in each group before adding the group to the model, and the number of variables are reduced further as groups are added. Since expressive masking will be measured at follow-up times as well, repeated measures

analyses are performed to estimate the relation between change in expressive masking and change in social self-management.

Aim 3: Moderating effect of gender

Models developed for Aim 1 and 2 are applied to explore in detail the effect of gender on the modeling results. For example, it may be found that rates of change in the study outcomes depend on both, expressive capacity at baseline and gender. The test of the moderating effect of gender on the relationship between expressive masking and social self-management in PD is conducted by stratifying the analysis and by including an interaction term between gender and potential predictors. For all models, non-linearities in predictors are tested, and variables are transformed when necessary to obtain good model fit. Models will be examined with respects to over-fitting and fine-tuned to improve their performance.

Problems and Alternative Strategies

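### No trajectory model is given a term for setting or contact mode, so a month-18 home effect or a phone effect would enter calendar-time curvature; the count of seven calls also needs reconciling

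*Combined protocol and SAP*

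**What the plan says.** **Visits.** Under Research design there are seven full assessments, "one at baseline and one every six months thereafter, with six in a clinical research lab and one in the home". Under Social networks, item 3 (Home visit), the timing is the same for all: "One assessment, scheduled approximately 1.5 years into the study, is in the home of each participant with PD".

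**Calls.** Research design adds: "Between the 6-month full assessments, there is an additional brief telephone call (15 to 30 minutes), totaling seven phone calls over three years". It gives the total as "This innovative design of 14 assessments over the three years". Under Brief telephone assessments a participant may choose another route, "such as a mailed questionnaire, if a telephone assessment is perceived as burdensome".

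**Analysis.** Models for longitudinal trajectories treats visits and calls as one series for three outcomes: "Outcomes measured at all 14 time points are: 1) physical and mental health scores (SF-12), 2) health quality of life with PD score (PDQ-8", with Social Isolation as the third. The same section says that the temporal dynamics of these outcomes will be explored. Aim 2 starts from a linear model with random intercept and slope, then adds demographic, clinical and other variables. Aim 3 adds: "For all models, non-linearities in predictors are tested". Neither setting (lab or home) nor mode (in person, phone or mail) is named as a model term, a covariate or the subject of a sensitivity analysis.

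**The concern.** Month 18 is the exact midpoint of 0 to 36 months, and it is the home visit for everyone. If answers given at home differ from answers given in the lab, the mean at that one visit moves for the whole cohort. A shift at the midpoint has almost no leverage on a straight line, but it has strong leverage on a quadratic term. An alternating phone-versus-visit difference does something similar, because both ends of the series are visits. Without a setting or mode term the model attributes either shift to time, and a change in how data were collected could be reported as a mid-study bump or dip.

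The documents offer one route by which this could happen. At the home visit the interviewer records a conversation about home and neighbourhood, guided by the modified CIRS. Recorded open-ended discussions from in-person sessions are transcribed for LIWC, whose dictionaries cover home as a topic, and LIWC proportions are a primary outcome. The plan does not say whether the home-visit conversation is kept out of that analysis.

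The number of calls is a separate matter. Seven visits do not leave room for seven calls if there is one between each pair.

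**Working it through.** **Schedule.** Visits fall at months 0, 6, 12, 18, 24, 30 and 36, which is 7. The intervals between them number 7 − 1 = 6, with midpoints at months 3, 9, 15, 21, 27 and 33. One call per interval gives 7 + 6 = 13 contacts, against 14 stated. The stated 14 is 7 + 7, which needs a seventh call outside those intervals or a second call within one. The documents describe neither.

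**Inputs from Power Calculation.** N = 120, ICC 0.82 (so within-person variance 1 − 0.82 = 0.18 in SD² units), dropout 15% per year, alpha 0.05. Two-sided testing and compound symmetry are my assumptions. The size d of any home or phone shift is not in the documents; 0.1 to 0.3 SD is an assumed range. The true trend is taken as linear.

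**Home shift, seven visits, complete data.** Let c = years − 1.5.
- Values of c² are 2.25, 1, 0.25, 0, 0.25, 1, 2.25, with mean 1.
- The sum of squares of (c² − 1) is 2(1.25²) + 2(0.75²) + 1 = 5.25.
- A shift d at c = 0 adds −d/5.25 = −0.190d SD/year² to the quadratic coefficient. By symmetry it adds 0 to the slope.
- SE = √(0.18/(120 × 5.25)) = 0.0169.
- For d = 0.1, 0.2 and 0.3 the ratios are 1.13, 2.25 and 3.38. The rejection probabilities are 20%, 62% and 92%.

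**Home shift, seven visits, 15% per year monotone dropout (expected GLS).** The quadratic coefficient is −0.189d with SE 0.0195. Fitted as a straight line, the slope bias is 0.019d SD/year.

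**Thirteen-point series, same dropout.** Per 1 SD of shift, the quadratic coefficient is −0.111 for home and −0.113 for phone, each with SE 0.016. The straight-line slope bias is about 0.010 SD/year for either.

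Probability of a falsely significant quadratic term, with dropout:

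| Assumed shift | Home, 7 visits | Home, 13 points | Phone v visit, 13 points |
|---|---|---|---|
| 0.1 SD | 16% | 11% | 11% |
| 0.2 SD | 49% | 29% | 30% |
| 0.3 SD | 83% | 55% | 57% |

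**Random slopes.** Because the plan has them, I added an assumed slope variance of 0.02 or 0.05. The complete-data figures do not change. With dropout the seven-visit figures become about 16%, 47–48% and 81–82%.

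**Scale.** For d = 0.2 the false curvature is about 0.038 SD/year². Over 1.5 years from the midpoint this is 0.038 × 1.5² ≈ 0.09 SD between the middle and the ends.

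**If the seventh call follows the last visit (month 39 assumed).** With 14 points spaced 0.25 year apart, the sum of squared time deviations is 0.25² × 14 × (14² − 1)/12 = 14.22. The calls sit on average 0.125 year later than the mean time, so their cross-product is 7 × 0.125 = 0.875. The slope bias is 0.875/14.22 ≈ 0.06 × shift per year. The phone effect then moves mostly out of curvature and into the slope.

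**Estimability.** Seven visit indicators plus a home indicator make 8 columns of rank 7, so the home term is aliased with month 18 under categorical time. Thirteen time indicators plus a phone term have rank 13 of 14. With a quadratic trend, home and phone terms are both estimable (rank 5 of 5).

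**The case against.** The strongest reply is that no stated hypothesis is harmed. For home shifts of 0.1 to 0.3 SD the slope bias over seven visits is 0.002 to 0.006 SD/year, against a planned detectable change of 0.40 SD/year. A shift common to all participants does not bias the expressive-capacity or gender contrasts either. This stands.

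A reader might infer that the plan's search for U-shaped courses would pick up the home visit as a finding. The documents do not support that. The U-shape remark is in the exploratory analysis of triggers, where time is re-centred on each person's own event, so month 18 falls at different offsets and a home effect would be largely scattered. The concern rests instead on calendar time: the exploration of temporal dynamics and the tests of non-linearity. Those are stated loosely. The sentence in Aim 3 is about predictors, and no quadratic-time test is specified. Time is nevertheless a predictor in every trajectory model.

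It is also fair that the list of further variables in Aim 2 is open-ended, so a setting term is not excluded, and that the planned plots of mean trajectories could show an isolated departure at visit 4. Neither commits the analyst to adjust for it.

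Finally, the shift sizes have no source in the documents. The rejection rates say what would follow from such an effect, not that one exists.

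**Conclusion.** The point holds as a gap in the analysis specification that is cheap to close. If answers depend on setting or mode, the models as written would express this as calendar-time curvature, with the false-positive rates tabulated above. Those rates rest on assumed shifts, compound symmetry, two-sided 5% tests and monotone dropout at the plan's rate. They concern claims about the shape of trajectories. The hypothesis of general decline is almost untouched by the home visit.

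On the count, a reader might conclude that 13 is right and 14 wrong. The documents show only that the two statements conflict. The slope bias of about 0.06 × shift per year arises only if the seventh call falls after the last visit, which is nowhere stated. Nor does the conflict reach the sample size, since Power Calculation is based on the seven full assessments.

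**What to change.** - **Mode.** Add an in-person versus remote term to the models of SF-12, PDQ-8 and Social Isolation, with phone and mail distinguished. Read the mail coefficient cautiously: participants who find calls burdensome choose mail, so it mixes mode with who chose it.
- **Setting.** For any claim about calendar-time curvature, fit a parametric time trend with a home indicator, or repeat the analysis without month 18. Do not interpret a month-18 departure that vanishes in that analysis. State that the home term cannot be estimated with categorical time.
- **LIWC.** State whether the home-visit conversation enters the word proportions.
- **Count.** Either state six calls and 13 time points, or state when the seventh call takes place.

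The cost is SAP wording plus a record of setting and mode at each contact. The statistical price is less information on mid-study curvature. In the seven-visit complete-data case, a home indicator leaves six visits to inform the quadratic term. The sum of squares falls from 5.25 to 12.25 − 7²/6 = 4.08, so the SE rises by a factor of √(5.25/4.08) ≈ 1.13.

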PD is documented to be more prevalent in men than women: 1.55 men for every woman [7]. To maximize the power of the hypothesis testing of gender differences (Aim #3) the plan is to oversample women, by targeting a gender distribution of 50% women (n = 60) and 50% men (n = 60) with the disease and their care partners, a maximum

combined total of 240 participants. Participants will be recruited through the BUMC Parkinson's Disease Movement Disorders Clinic, postings on PD and aging research and advocacy websites, and PD support groups in the urban, suburban and rural regions within driving distance of the Boston metropolitan area.

Eligibility screening

Individuals who respond to recruitment are screened in a 1-hour session by a movement disorders neurologist and movement disorders nurse specialist for eligibility and to collect demographic data and conduct a medical history protocol. Informed consent procedures are conducted prior to screening for eligibility and consenting participants sign the BUMC consent form. Before their baseline assessment, participants sign their Tufts University consent form. Screening and assessments take place at the BUMC Parkinson's Disease and Movement Disorders Center or at the Tufts University Health Quality of Life Lab in Medford.

Inclusion criteria for participants with PD ensure minimal capacity to participate in the study procedures:

1. Diagnosis of idiopathic PD utilizing the UK Parkinson's Disease Society Brain Bank clinical diagnostic criteria, as evaluated by the neurological team,
2. Modified Hoehn and Yahr stage 1 through 4,
3. Score \geq 26 on the Mini-Mental Status Exam,
4. Home setting within travel distance to study locations,
5. Able to communicate clearly and in English with research staff,
6. Interested in participating and willing and able to provide informed consent.

Inclusion criteria for care partners are very flexible since participation of a care partner, while desired, is not required:

1. Person with PD must consent for care partner to participate,
2. Score ≥ 26 on the Mini-Mental Status Exam,
3. Able to communicate clearly and in English with research staff,
4. Interested in participating and willing and able to provide informed consent.

Baseline and 6-month follow-up in-person assessment procedures

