The data analysis assumes 120 participants with PD and seven full assessment time points over three years; dropout per year at 15%; intra-class correlation (ICC) at 0.82, based on prior data [43]; and type I error at $\alpha=0.05$. These metrics predict 80% power to detect a mean change over time of 0.40 of a standard deviation in the PDQ-39 outcome per year; 80% power to detect a correlation between continuous variables of 0.23; and 80% power to detect a difference of 0.50 standard deviations in the outcome scale between genders (Aim 3). Previous studies of similar outcomes have found a

sample size of 120 to be adequate for demonstrating statistically significant effects [43, 44].

Data analysis

Aim 1: Social self-management trajectories

Descriptive analyses

Descriptive statistical analyses will be performed on the total sample and on demographic subgroups that are relevant to the progression of Parkinson's disease (e.g., current age, age of onset, disease severity at baseline, gender). Mean trajectories over time will be plotted for all repeated measures by the same demographic subgroups. Scales will be checked for floor and ceiling effects. Associations between the scales, which represent the different components of social self-management, will be examined through scatter plots and relational statistics.

Audiotaped open-ended discussions during in-person and telephone assessment sessions will be transcribed. Quantitative content analysis will be performed on the transcriptions using Linguistic Inquiry Word Count (LIWC) to describe proportions of verbal content meaningfully related to the three ICF social self-management categories in the study's model [45]. LIWC contains word dictionaries that measure 80 language dimensions including psychological constructs (e.g. affect, cognition), biological processes (e.g. body, health), personal concerns (e.g., social, home, work, leisure) and linguistic indicators of socio-emotional experience and interpersonal interaction. The dimensions have been validated in over 120 published studies as indicative of a variety of life preferences and health outcomes [46] and in previous work on motivation indicators (e.g., helplessness, hopefulness, apathy) in PD [40]. Verbal content

proportions from the LIWC analysis will be included with quantitative questionnaire results that are entered into quantitative descriptive and longitudinal analyses.

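### The 80% power figure labelled Aim 3 is for a difference between genders in the outcome, whereas Aim 3 tests whether gender moderates the effect of expressive capacity on change, and no power is given for that test

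*Combined protocol and SAP*

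**What the plan says.** Specific aim 3, in the Background, is to "Determine the moderating effect of gender on the association between expressive capacity in PD and change in social self-management". The hypothesis beneath it is directional: women's trajectories are expected to be more vulnerable to expressive disability than men's.

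The Power Calculation section gives three figures. The one assigned to this aim is "80% power to detect a difference of 0.50 standard deviations in the outcome scale between genders (Aim 3". The one closest to Aim 2 is "80% power to detect a correlation between continuous variables of 0.23". The inputs are introduced with "The data analysis assumes 120 participants with PD and seven full assessment time points over three years", followed by 15% dropout per year, an ICC of 0.82 and a type I error of 0.05. Sidedness is not stated.

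The Recruitment section justifies oversampling women by the power to test gender differences under Aim 3, with a target of "50% women (n = 60) and 50% men (n = 60) with the disease".

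Under Data analysis, the Aim 3 section applies the models built for Aims 1 and 2 and says that the test of moderation "is conducted by stratifying the analysis and by including an interaction term between gender and potential predictors". Nowhere does the document give an interaction size, a variance of individual slopes, or a power for the moderation test.

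**The concern.** The figure labelled Aim 3 contains neither expressive capacity nor change. It is a main effect of gender on the outcome. A moderation effect is a difference between two associations and is estimated less precisely than either the overall association or, for effects of ordinary size, a difference in means.

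Aim 3 is one of three specific aims and shaped the sampling plan. If the interaction turns out null, a reader who relies on the Power Calculation could take it as evidence against moderation from a test with 80% power. The document gives no basis for that reading. The analysis text also names two procedures, stratification and an interaction term, without saying which decides the question, and does not write out the term.

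**Working it through.** **Inputs from the document.** Power Calculation: 120 participants with PD, seven full assessments over three years, ICC 0.82, dropout 15% per year, alpha 0.05. Recruitment: 60 women and 60 men.

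**Assumptions added here.** Two-sided testing; monotone dropout with a fraction 0.85^t remaining at t years; expressive capacity standardised, with the same spread in both genders and unrelated to gender; slope SD as shown in step 5. Power is Φ(effect/SE − 1.96), and the detectable effect at 80% power is 2.80 × SE.

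**1. The plan's own figure.** For two groups of 60 and one measurement each, SE = √(2/60) = 0.183 SD. Then 0.50/0.183 = 2.74 and Φ(2.74 − 1.96) = 78.2%. The stated 80% is reproduced within two points as a simple comparison of means.

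**2. Same contrast with repeated measures.** A person with k visits contributes k/(1 + (k − 1) × 0.82) to the effective sample size. Averaged over the dropout pattern, this gives 138.8 in total, or 69.4 per gender. SE = √(2/69.4) = 0.170, and power for 0.50 SD is Φ(2.95 − 1.96), about 84%. The arithmetic behind the sentence is therefore sound; the quantity is the wrong one for Aim 3.

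**3. Interaction against overall effect.** For a standardised predictor, the overall effect has SE σ/√N. Within each gender it is σ/√(N/2). The difference between genders has SE √(2σ²/N + 2σ²/N) = 2σ/√N, twice the overall SE. The same ratio holds when the outcome is each person's slope, because the slope variance enters both SEs equally and cancels.

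**4. Illustration on level.**
- Overall association: 2.80/√138.8 = 0.238, close to the plan's 0.23.
- Gender difference in association: 2 × 0.238 = 0.476, about 0.48.
- Power if the genders differ by 0.23: 0.23/0.170 = 1.355, and Φ(1.355 − 1.96) = 27%.
- Cross-check by Fisher's z, one measurement, 60 per gender, correlations 0.23 and 0: arctanh(0.23) = 0.234; SE = √(2/57) = 0.187; Φ(1.25 − 1.96) = 24%. The correlations detectable with 80% power are 0 and 0.48. For 0.23 and 0, 80% power needs 2 × (2.80/0.234)² + 3, about 290 per gender.

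**5. Illustration on change, the scale of the aim.** Mixed-model (GLS) information with intercept variance 0.82, residual variance 0.18, uncorrelated slope SD τ, and the dropout above. The 14-point columns assume quarterly contacts from 0 to 3.25 years.

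| τ (SD/year, assumed) | Detectable overall effect on slope, 7 visits | Detectable gender difference, 7 visits | In slope SDs, 7 visits | In slope SDs, 14 points | Power for 0.23 slope SDs, 7 / 14 |
|---|---|---|---|---|---|
| 0.1 | 0.058 | 0.115 | 1.15 | 0.92 | 8% / 10% |
| 0.2 | 0.077 | 0.154 | 0.77 | 0.68 | 13% / 15% |
| 0.3 | 0.100 | 0.200 | 0.67 | 0.62 | 16% / 18% |

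Columns two and three are in SD/year per SD of expressive capacity, and the third is twice the second, as step 3 requires. Worked entry, τ = 0.1 and seven visits: the overall SE is 0.058/2.80 = 0.0206, so the interaction SE is 0.041; the effect is 0.23 × 0.1 = 0.023; Φ(0.56 − 1.96) = 8%.

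**The case against.** Four points can be made for the plan.

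- **The shortfall depends on effect size.** With expressive capacity standardised, the interaction on level has the same SE (0.170) as the gender difference in means. An interaction of 0.50 outcome SD per SD of expressive capacity would therefore also have about 84% power. This stands. A reader might infer that the design has far less power than claimed for Aim 3 whatever the truth; the documents do not support that, because they give no moderation size. But 0.50 means associations of roughly 0 in one gender and 0.5 in the other, which is very large, and it still concerns level.
- **Change is modelled.** A reader might infer from the wording of the interaction that the plan tests moderation of level only. The Aim 3 section applies the Aim 1 and 2 models, which are multilevel models for change with random intercepts and slopes, and its own example has rates of change depending on both expressive capacity and gender. A three-way term is implied; it is not written out.
- **An interaction is planned.** A reader might infer that moderation will be judged by comparing significance between the two strata. The section says the test is conducted "by stratifying the analysis and by including an interaction term between gender and potential predictors" and nowhere proposes that comparison. What is open is which of the two decides.
- **Some outcomes have 14 time points.** SF-12, PDQ-8 and Social Isolation do. This improves the detectable values, as the table shows, but only modestly, because with more measurements the true variation in slopes between people dominates.

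The document also speaks of exploring the effect of gender and notes the lack of precedents. That is fair caution, but it does not disclose the power of the test.

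**Conclusion.** The power statement is attached to the wrong quantity. It describes a gender main effect, and no power is stated for the moderation that Aim 3 sets out to test. This follows from the text alone.

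The factor of two between the detectable moderation on slope and the detectable overall expressivity effect on slope does not depend on the slope variance. It does rest on the balanced split and on similar spread of expressive capacity and similar dropout in both genders.

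The absolute figures are illustrations. Those on level use the plan's inputs with two-sided testing assumed. Those on change also rest on an assumed slope SD of 0.1–0.3 SD/year, for which the document gives no value. Across that range the detectable difference is about 1.15 to 0.67 slope SDs with seven visits and 0.92 to 0.62 with 14 points. Power is low for moderation clearly below these values and adequate at or above them.

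**What to change.** - In the Power Calculation, relabel the 0.50 SD figure as a gender main-effect comparison.
- For Aim 3, state the detectable gender by expressive capacity by time interaction, with the slope variance assumed, the sidedness and the number of time points.
- In the Aim 3 analysis section, write out that three-way term and name it, with its 95% confidence interval, as the deciding test. Present gender-stratified fits as description.
- Say that Aim 3 has limited power unless moderation is large.

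The cost is a recalculation and some wording. The stated figure becomes less favourable. No new participants, visits or data are needed.
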